2.2 Study Agents

The investigational agent for this study, panitumumab-IRDye800, is unapproved by FDA, and an Investigational New Drug application (IND) is required for this study. [Note: the antibody moiety of the investigational agent is approved by FDA as Vectibix (panitumumab)]. Lymphoseek is an FDA-approved agent for oral cavity SNB.

This protocol will be added to existing IND-119474 (IND Holder: [name]).

2.3 Rationale

Overall impact of the proposed study on surgical oncology: Introduction of this technology to the operating room in the manner we propose would represent a paradigm shift in oncologic surgery as there are currently no techniques available that allow intraoperative detection of metastatic LNs. The use of optical imaging would be a significant improvement in real-time identification of cancer in LNs.

Our study would demonstrate important proof-of-principle and translate concepts that molecular biologists have used for more than a decade to identify and label cancer in real-time. At the same time it will allow us to evaluate the value the panitumumab-IRDye800 approach can have when compared to the current standards.

Not only can this have strong impact on subjects with HNSCC, the development of a cancer specific contrast agent of this type can also be applied to other solid tumors that express EGFR for which LN status of prognostic value. Furthermore, if the principle of targeted optical imaging is validated using EGFR, other therapeutic antibodies could be assessed for imaging potential. Successful completion of this study will thus have a lasting impact on the field of surgical oncology.

Our proposed study offers the potential to improve current standard of care in the following ways:

1. **Despite the variety of techniques available for metastatic LN detection, consensus is lacking (46,68)**
2. **Currently no intraoperative technique is available to directly identify tumor-positive LNs:** Panitumumab-IRDye800 has already shown to allow for real-time fluorescence imaging of the primary tumor (IRB-35064).
3. **Real-time feedback:** Presence of regional disease can be assessed intraoperatively.
4. **Minimally-invasive approach:** Presence of regional disease can be assessed intraoperatively, leading to fewer healthy LNs removed.
5. **Use in other cancer types:**
 - EGFR is highly-expressed in multiple cancer types, allowing application to other tumor types beyond HNSCC.
 - Our proposed technique can even be extended to tumors that are not accessible for superficial injections for SNB but for which LN status plays an important role, eg, colorectal cancer.

6. High feasibility: We have previously conducted dose-escalation phase 1 clinical trials using cetuximab-IRDye800 and panitumumab-IRDye800 in HNSCC ((69) and (65,68), respectivley).

2.4 Study Design

- The primary purpose for the protocol is **Image Guidance**. The primary objective of the study is to determine if near-infrared fluorescence imaging of panitumumab-IRDye800 can identify metastatic disease in regional neck LNs of subjects with HNSCC.
- There are **2 cohorts**.
- The study is **open-label**. No masking is used.
- The study is **non-randomized**.
- The primary outcome is **number and location of LNs that are near-infrared fluorescent and that contain tumor as defined by (histo-)pathology**.

The study is an open-label study to determine if near-infrared fluorescence imaging of panitumumab-IRDye800 can identify metastatic disease in regional neck LNs of subjects with HNSCC. Panitumumab-IRDye800-based findings will be compared to LN biopsy and neck dissection. A schematic overview of the clinical trial is given in Figure 1.

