Typically, to identify the SN(s) preoperatively, a local injection of a non-tumor specific radiotracer is given around the primary tumor followed by lymphoscintigraphy to visualize

drainage of the radiotracer through the lymphatic system to the SN(s) (20–22). The addition of single photon emission computed tomography combined with computed tomography (SPECT/CT) was shown to allow for localization of the SN within its anatomical context, providing the surgeon with a 3D map to plan the surgical procedure (22). During the surgical procedure, these SN(s) can then be identified and excised using a gamma ray detection probe that localizes the radioactive signal in the nodes (20,23). More recently, mobile gamma cameras were introduced to provide the surgeon with additional (visual) feedback with regard to having localized and removed the radioactive LNs (24).

Meta-analysis of SNB in breast cancer, head and neck cancer, and melanoma have validated the accuracy of SNB in predicting occult LN metastasis (13,17,25,26). More recently, for HNSCC, the validity of the approach was also shown. In a large multicenter study including 227 SNB procedures from 6 centers, Alkureishi *et al.*, showed that the procedure was successful in 93% subjects whereby in 34% (42 subjects) of cases HNSCC subjects were upstaged whereby in 10 subjects only micro-metastasis were present (27). Where the centers participating in the Alkureishi *et al.*, paper used colloid-based SN tracers, more recently a mannose-receptor targeting tracer for SNB was introduced, Lymphoseek (28–34). In head and neck cancer, using Lymphoseek an even higher sensitivity was reported: in 98% of subjects (81/83) at least one SN could be found with false-negative rate of 2.6% (ie, tumor-positive LN was not detected by Lymphoseek) and a negative predictive value of 98% (28).

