Sentinel node biopsy vs elective regional node dissection: Besides decreased morbidity, SNB offers other advantages over a neck dissection: i) Identification of aberrant draining patterns and “skip metastasis” (35–37); and ii) Improved (micro-) metastasis identification at (histo-)pathology; fewer SNs are harvested which are more meticulously evaluated by the pathologist, resulting in improved diagnostic accuracy (38,39). However, challenges remain: i) Local tracer injection is complicated in areas deep in the oral cavity; ii) Near-injection site SN identification can be challenging due to overshadowing of signal at the primary tumor signal (40,36,22); iii) Often multiple SNs are identified during surgery (22) increasing the risk of complications (41) (eg, nerve damage, lymphedema, scar tissue formation); iv) neck dissection after a positive SNB is complicated due to the presence of scar tissue; and v) A false-negative SNB occurs in 3 to 10% of subjects (ie, the SN is tumor-negative, but at follow-up metastasis in remaining regional LNs are found (42–45). Moreover, although LN mapping is superior to radiographic and clinical exam, it is still limited by the need for direct injection of the dye or radiolabeled compound. **Upstaging with LN assessment can thus only be assessed in tumor types that are accessible for local injection.** This is significant because it influences standard of care (LN surgery or complete lymphadenectomy) in these subject populations only. Identification of regional disease will inform prognostic information and/or determine the need and extent of adjuvant therapies for additional tumor types. Most importantly, however, the tracers used for SNB are not tumor-specific and thus SNB, similar to neck dissection, does not allow for intraoperative tumor-positive LN identification (21,46,47). In fact, **for both SNB and neck dissection (histo-)pathological evaluation is required to determine the presence of (micro-) metastasis and thus a method to intraoperatively identify metastatic LNs is lacking.** Thus, HNSCC subjects would benefit from an alternative technique that, allows for intraoperative lymph node staging.

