3. Hereafter, as per standard of care, the surgeon will perform SNB using the gamma probe. For this, the surgeon will evaluate the neck with the gamma probe for the presence of radioactive nodes. Upon localizing of radioactive nodes, the count rate of the node will be determined. Then, just prior to the resection of the radioactive node, *in situ* fluorescence imaging will be performed to evaluate the fluorescence-based visibility of the node. For each radioactive node, the respective *in situ* location will be documented (level Ia, Ib, IIa, IIb, III, IV or V) as well as the radioactive status (count rate) and fluorescence status (yes/no). Hereafter the node will be harvested by the surgeon. This process will be repeated until no radioactive nodes are detected anymore *in situ*.

Step 2) Wound bed imaging:

As per standard of care SNB, upon completion of SNB, the neck will be screened once more with the gamma probe as such to determine the presence of any remaining radioactivity (ie, a radioactive signal detected > 10% of the background that correlates with any substrate (node). Areas in the wound bed determined radioactive-positive will be surgically re-evaluated, and, upon checking the fluorescence-status, removed, if deemed necessary by the surgeon. If any nodes are found, gamma tracing will be performed to determine the radioactive status.

Step 3) Pathological imaging:

The fluorescence and/or radioactive status of all excised nodes will be confirmed *ex vivo* on the back table using both a closed-field imaging device and an open-field device as well as the gamma probe, respectively. Hereafter all excised nodal specimens will be sent for (histo-)pathology. After the tissue has been processed and evaluated by the pathologist, imaging findings will be compared to gold-standard histological-assessment performed by the pathologist (including a hematoxylin and eosin (H&E) staining) to determine the correlation between fluorescence, radioactivity and the presence/absence of tumor tissue in the LN(s). Also findings will be compared to preoperative lymphoscintigraphy and SPECT/CT imaging (ie, correlation between preoperative imaging findings and intraoperative imaging findings).

Neck dissection only (T1-4, cN+)

After the neck has been opened by the surgeon, it will be inspected by the surgeon for the presence of suspicious nodes. Real-time fluorescence imaging of the LNs in the neck will then be performed at 4 time points:

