Step 1) *In situ* imaging: After having opened the skin and exposure of the neck LNs, *in situ* fluorescence imaging will be performed to evaluate the fluorescence-based visibility of the LNs. For each fluorescent LN, the respective location will be documented (level Ia, Ib, IIa, IIb, III, IV or V) after which it will be harvested by the surgeon. This process will be repeated until no fluorescent LNs are seen *in situ*. Hereafter, the standard of care completion neck dissection will be performed.

Step 2) *Ex vivo* imaging: The neck dissection specimen will be evaluated for the presence of fluorescent LNs using both a closed-field imaging device and an open-field device. All additional fluorescent LNs will be identified, documented and collected separately; we acknowledge that the penetration depth of the fluorescence signal is limited and therefore deeper located LNs might not be detectable *in situ* (under step 1), but after having taken out the specimen and having “flipped” the specimen this might be possible.

Step 3) Wound bed imaging: This will be conducted for any remaining fluorescence (ie, any remaining fluorescent LNs). Areas in the wound bed determined fluorescence-positive will be surgically re-evaluated, and, if deemed necessary by the surgeon, removed.

Step 4) Pathological imaging: All excised nodal specimens will be imaged once more in the closed-field device to confirm that all fluorescent LNs have been removed from the neck dissection specimen. If not, the number and location of remainder fluorescent LNs will be documented after which they will be harvested; we will use the image taken under step 2 for reference as such to make sure that we did not create any confounding factor due to tissue

preparation to harvest nodes at step 2. Hereafter all excised nodal specimens will be sent for (histo-)pathology. After the tissue has been processed and evaluated by the pathologist, fluorescence imaging-based findings will be compared to gold-standard histological-assessment performed by the pathologist (including a hematoxylin and eosin (H&E) staining) to determine the correlation between fluorescence and the presence/absence of tumor tissue in the LN(s).

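### Cohort 2 nodes are sorted by fluorescence before histology, and nothing masks the pathologist to fluorescence or requires one work-up for all nodes

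*Combined protocol and SAP*

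**What the plan says.** Section 2.4 (Study Design) lists the trial as open-label and adds "No masking is used". It makes no exception for the reading of pathology.

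Section 2.4.3.3 describes the neck dissection cohort (Cohort 2, cN+) in four steps:

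- **Step 1, in situ:** "For each fluorescent LN, the respective location will be documented", and the node is then harvested. This continues until no fluorescent node is seen. The completion dissection follows.
- **Step 2, ex vivo:** "All additional fluorescent LNs will be identified, documented and collected separately".
- **Step 3, wound bed:** areas that still fluoresce are re-evaluated and removed if the surgeon judges it necessary.
- **Step 4, pathological imaging:** specimens are imaged again to confirm that no fluorescent node remains in the dissection specimen, and any that do are harvested. Then: "Hereafter all excised nodal specimens will be sent for (histo-)pathology". Fluorescence is compared with the "gold-standard histological-assessment performed by the pathologist", which includes H&E.

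Cohort 1 differs. Nodes are taken on radioactivity, with fluorescence recorded as yes or no: "This process will be repeated until no radioactive nodes are detected anymore".

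Section 12.1.1 answers the primary objective with node-level sensitivity and specificity against histology. Section 12.1.2 singles out false negatives as a particular concern. No section describes specimen coding, what the requisition shows, or a sectioning rule common to all nodes.

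**The concern.** The reference standard should be equally able to find tumour whatever the index test showed. In Cohort 2 the index test decides how a node leaves the neck: fluorescent nodes come out individually or are set aside, and non-fluorescent nodes are what remains in the dissection specimen. With an unmasked reader and no common work-up, the two groups could be searched with different intensity.

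The background gives a reason to take this seriously. In comparing sentinel node biopsy with neck dissection, Section 2.1 says that "fewer SNs are harvested which are more meticulously evaluated by the pathologist, resulting in improved diagnostic accuracy". The comparison is a different one, but it shows that the authors accept that search intensity changes what is found.

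A metastasis missed in a non-fluorescent node moves from false negative to true negative. Sensitivity then looks better than it is, specificity rises slightly, and the hidden errors are the ones the plan cares most about. Differential work-up cannot readily be undone once the nodes have been read.

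**Working it through.** **The plan's own figures (Section 12.1.3).** With 600 nodes from 20 subjects there are 30 nodes per subject, so the effective sample size is 600 / [1 + (30 − 1) × 0.005] = 600 / 1.145 = 524.0, against a stated 524. Power for the 0.1 specificity difference comes out at 99.3 to 99.8% (stated: above 99%). One-sided exact McNemar power for the 0.2 sensitivity difference is 78.2% with 40 positive nodes and 76.8% with 39; a normal approximation with 39.3 gives 82.7% (stated: above 78%). The stated figures reproduce. None depends on masking, so this point changes no sample-size figure; it concerns bias.

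**Inputs for the bias.**

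- True sensitivity Se: 0.75, the lower sensitivity in Section 12.1.3, with 0.85 as a second case (assumed).
- Positive nodes: 7.5% × 600 = 45 (Section 12.1.3).
- d1 and d0: the probabilities that pathology finds a metastasis present in a fluorescent and in a non-fluorescent node. The documents give neither. Set d1 = 1 and let d0 run from 1 to 0.5 (assumed).

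**Formula.** Observed Se = Se·d1 / [Se·d1 + (1 − Se)·d0]. Only the ratio d0/d1 matters, and equal work-up (d0 = d1) returns the true value.

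**Results.** At Se = 0.75 the 45 positive nodes split into 33.75 true positives and 11.25 false negatives. The number hidden is 11.25 × (1 − d0).

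| Missed in non-fluorescent nodes (1 − d0) | Observed, true Se 0.75 | Observed, true Se 0.85 | False negatives hidden, of 11.25 |
|---|---|---|---|
| 0% | 0.750 | 0.850 | 0 |
| 10% | 0.769 | 0.863 | 1.1 |
| 20% | 0.789 | 0.876 | 2.2 |
| 30% | 0.811 | 0.890 | 3.4 |
| 50% | 0.857 | 0.919 | 5.6 |

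For example, at 50% missed: 0.75 / (0.75 + 0.25 × 0.5) = 0.75 / 0.875 = 0.857.

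**Specificity.** Take the lower specificity of 0.8 and 600 − 45 = 555 negative nodes, so 444 true negatives. Adding 5.6 hidden metastases gives (444 + 5.6) / (555 + 5.6) = 0.802. The effect is negligible.

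**Scope.** The table treats all 45 positive nodes as exposed to the sorting. Sorting by fluorescence is described only for Cohort 2. The documents do not split positive nodes by cohort, so for a pooled estimate the table is an upper bound at each assumed miss rate; positive nodes from Cohort 1 would dilute the effect.

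**The case against.** The case on the other side has real force.

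**Nothing says the pathologist is told.** A reader might infer that fluorescent nodes are submitted separately, that the pathologist knows the result, and that histology is therefore more sensitive in fluorescent nodes. The documents support none of these as fact. The text says collected separately, then that all nodes go to pathology; labelling is not described. The masking sentence is a general design bullet. This objection stands: what can be said is that the reader is not stated to be masked.

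**Several sections point to routine pathology.** Section 4.5 says the imaging will not inform diagnosis or medical decisions. Section 2.4.3.4 says laboratory imaging will not alter standard processing, Section 2.4.3.5 refers to standard procedures, and Section 9.2.4 places an optical scan after the clinical pathology assessment. These make differential work-up less likely. They do not mask the reader, set a common work-up, or undo sorting that took place at surgery.

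**Section 2.1 compares two operations.** Its remark on closer examination concerns sentinel nodes against neck dissection nodes, not fluorescent nodes within one dissection. It makes the mechanism plausible and no more.

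**A larger, firmer size is tempting.** Section 2.1 reports 42 upstaged subjects, of whom "in 10 subjects only micro-metastasis were present", so 10/42 = 24%. If micrometastases were 24% of positive nodes and were all found in fluorescent and none in non-fluorescent nodes, a true 75% would appear as 0.75 / (0.76 + 0.24 × 0.75) = 79.8%. With sensitivities of 85% for macro- and 40% for micrometastases (no source), the true value is 0.76 × 0.85 + 0.24 × 0.40 = 74.2% and the apparent one 0.742 / (0.76 + 0.24 × 0.40) = 86.7%. A reader might conclude that the bias is 5 to 13 points. That is an extreme case. If half were missed, the same approach gives 0.75 / 0.97 = 77.3% and 0.742 / 0.928 = 80.0%, about 2 to 6 points. The 24% also counts subjects, not nodes, and comes from sentinel node biopsy, not from cN+ necks.

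**The study is small.** Section 2.4.1 calls it exploratory. With 45 positive nodes the 95% half-width at 75% is 1.96 × √(0.75 × 0.25 / 45) ≈ 0.13 before clustering, wider than the bias in every row of the table. That limits the weight of the point. Unlike sampling error, though, the bias has a known direction if work-up differs, and the confidence interval does not show it.

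**Conclusion.** The point holds as a gap in the protocol. Cohort 2 nodes are sorted by the index test before the reference standard is applied, no section masks the reader to fluorescence, and no section requires one work-up. If fluorescent nodes are examined more closely, sensitivity is biased upward.

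The size cannot be derived from the documents. Under the assumption that 0 to 50% of metastases in non-fluorescent nodes are missed and none in fluorescent nodes, a true 75% would appear as 75 to 86%, hiding between none and about 6 of some 11 false negatives. The lower end is no bias at all, which is what routine, even-handed pathology would give. For a pooled estimate over both cohorts the effect would be smaller, by an amount that depends on the unknown share of positive nodes from Cohort 1.

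This is a cheap improvement. It does not show that the results will be biased, and it does not touch the sample size or power.

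**What to change.** In Sections 2.4 and 2.4.3.3 (neck dissection, Step 4), state that the pathologist reading the nodes is masked to fluorescence status. To put this into practice:

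- Send nodes under neutral codes giving anatomic level only, with no fluorescence result on the requisition.
- Apply the same routine H&E work-up to every node, fluorescent or not.
- Have the imaging team hold the fluorescence record and link it to histology after sign-out.
- In Section 12.1.1, base the primary sensitivity and specificity on that uniform reading, and report metastases found only by extra sectioning separately.

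Leave the handling of sentinel nodes in Cohort 1 as it is. Those nodes are harvested because they are radioactive, so hiding gamma status would achieve little.

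The cost is some labelling and a link list. Masking will be partial, because nodes harvested singly may still be recognisable beside the bulk specimen. The common work-up therefore matters more than the codes: with equal detection in both groups, the formula above returns the true sensitivity.

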2.4.1. Number of subjects

A total of 20 subjects will be enrolled in our exploratory study.

Rationale for including cN0 and cN+ subjects: Based on NCCN guidelines, version 1 2018, SNB is justified in subjects with a T1 or T2 stage primary tumor and a cN0 neck that are at (high) risk for having LN metastasis. The strength of SNB lies in the identification of “skip lesions” (ie, metastatic spread to a LN outside the expected drainage area) and aberrant drainage patterns (ie, drainage to LNs that are outside the expected drainage template) (12-14). Including cN0 subjects will thus provide us with the unique opportunity to directly compare the performance of panitumumab-IRDye800 for metastatic LN identification to that of Lymphoseek and thus validate our approach against the reference standard.

Panitumumab-IRDye800 will be evaluated in subjects with any T stage and a cN+ neck to study how well panitumumab-IRDye800 can detect metastatic lesions in the LN(s).

2.4.2. Dosing

Subjects will be infused with 50 mg panitumumab-IRDye800 and 2 mCi Lymphoseek. Panitumumab-IRDye800 will be systemically infused 1 to 5 days prior to surgery, whereas 2 mCi Lymphoseek will be administered locally on the day before surgery (Table 1).

Table 1: Cohort structure

Cohort	Preoperative nodal stage	Number of subjects	Dose panitumumab-IRDye800	Dose Lymphoseek
1	T1 or T2 stage and node negative (ie, cN0)	10	50 mg	2 mCi
2	Any T stage and node positive (ie, cN+)	10	50 mg	none

2.4.2.1. Rationale for panitumumab-IRDye800 dosing

The dose we use in the current study is derived from the optimal dose as determined in Stanford IRB protocol IRB-35064 whereby we evaluated the safety and dosing of panitumumab-IRDye800 in HNSCC. In this study, we also investigated the necessity of an unlabeled-panitumumab loading dose. We found no significant differences in fluorescence intensities around the primary tumor site and similar TBRs when no loading dose was administered. Moreover, the 50 mg dose was found safe (no Grade 2 or greater toxicity reported) and easy to administer (unpublished data; see safety reports IRB-35064).

